7.6.3.5 Proportion of subjects with adjudicated cardiovascular endpoints

The analysis of proportion of subjects with adjudicated cardiovascular endpoints, including cardiovascular death, nonfatal myocardial infarction, nonfatal stroke, hospitalization for unstable angina, hospitalization for cardiac failure, and urgent or emergency visits for heart failure at Week 48, Week 96, and end of study will be performed using the FAS. A CMH test will be used to compare the differences in proportions of subjects with adjudicated cardiovascular endpoints between the EFX arms and the placebo arm, adjusting for stratification factors. The point estimates and 95% CIs for the differences in proportions, and p-values will be calculated. The 95% CI will be constructed using the Miettinen and Nurminen method. In addition, the odds ratio and risk ratio point estimate and 95% CI will be summarized for each EFX arm compared to placebo.

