1.4.1.1. Subject Disposition

In the Main Study, eligible subjects were randomized to receive 28, 50, or 70 mg EFX or placebo in a ratio of 1:1:1:1. The planned sample size was approximately 80 subjects. EFX or equivalent dose of placebo was administered QW for 16 weeks.

A total of 80 subjects were enrolled with 79 subjects receiving at least one dose of study drug. A total of 66 subjects (82.5%) completed investigational product as per the dosing regimen for 16 weeks. Thirteen subjects (16.3%) discontinued investigational product (4 subjects in 70 mg EFX, 4 subjects in 50 mg EFX, 3 subjects in 28 mg EFX and 2 subjects in the placebo group). Seven subjects discontinued investigational product because of AEs and 7 subjects (9.0%) discontinued the study due to administrative reasons. A total of 66 subjects (82.5%) completed the study.

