3.3. Early Termination

If discontinuation of study drug occurs, the subject should return to the clinic within 5 days to perform the Early Termination (ET) assessments.

Subjects with ongoing clinically significant clinical or laboratory findings will be followed until the finding is resolved or medically stable; reasonable attempts will be made to follow up with subjects. The subject's participation will end once all study assessments and the 30-Day Follow-up visit has been completed.

The ET assessments are outlined in the Schedule of Assessments ([Appendix A - B](#)).

3.4. 30-Day Follow-up

The 30-Day Follow-up visit should be completed 30 days following the last dose of study drug received.

The 30-Day Follow-up assessments are outlined in the Schedule of Assessments ([Appendix A - B](#)).

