5.3 Full Analysis Set

The analysis set for non-histological efficacy analyses will be the FAS which will include all subjects who were randomized into the study.

Subjects who receive a dose of study drug other than that to which they were randomized for the entire duration of treatment will be analyzed according to the treatment group to which they were randomized.

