6.2 Handling of Dropouts, Missing Data, and Outliers

Subjects in the FAS with missing liver biopsy data will be considered as non-responder in the analyses of histological endpoints on the FAS. With these exceptions, values for missing data will not be imputed unless specified. The same handling of missing liver biopsy data will also be applied for the MFAS, which is a subset of the FAS.

Where appropriate, safety data for subjects who did not complete the study will be included in summary statistics. For example, if a subject received study drug, the subject will be included in a summary of AEs according to the treatment received; otherwise, if the subject is not dosed then they will be excluded from the summary.

If safety laboratory results for a subject are missing for any reason at a time point, the subject will be excluded from the calculation of summary statistics for that time point. Values for missing safety laboratory data will not be imputed; however, a missing baseline result will be replaced with a screening result, if available. If no pre-treatment laboratory value is available, the baseline value will be assumed to be normal (i.e., no grade [Grade 0]) for the summary of graded laboratory abnormalities.

Values for missing vital signs data will not be imputed; however, a missing baseline result will be replaced with a screening result, if available.

Below limit of quantification (BLQ) PK concentration at pre-dose at Baseline will be imputed as zero and the other pre-dose BLQ PK concentrations will be imputed as half of the low limit of quantification (0.5*LLOQ).

No rules for outlier detection are planned.

CONFIDENTIAL

7. Statistical Methods

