7.1 General Principles

All data processing, summarization and analyses will be performed using Fortrea's SAS Environment / Version 9.4 (or later) of the SAS® statistical software package.

The following principles will be applied to all tables, figures, and listings (TFLs) unless otherwise stated:

Principle	Value
Significant tests	Two-sided and use a 5% significance level for main effects and 10% significance level for interaction terms.
Treatment group labels and order presented	Placebo EFX 28 mg EFX 50 mg All EFX (as applicable) Total (as applicable)
Tables	Data in summary tables presented by assessment or parameter, treatment group, and visit (where applicable).
Listings	All individual subject data will be listed as measured and presented by treatment group, subject, and visit (where applicable), unless otherwise specified.
Descriptive summary statistics for continuous variables	Number of non-missing values (n), arithmetic mean, arithmetic standard deviation (SD), median and range (minimum and maximum). Descriptive statistics for certain continuous data will include geometric mean and geometric coefficient of variation. PK concentrations will be summarized with the set of continuous parameters including geometric mean and will add the statistic of number of samples below the limit of quantification (BLQ).
Descriptive summary statistics for categorical variables	Frequency counts and percentages [n (%)].
Denominator for percentages	Number of subjects in the analysis set, unless stated otherwise in table shell.
Include "Missing" as category	Demographics and Other Baseline Characteristics only.

Statistical Analysis Plan

Sponsor Name: Akero Therapeutics, Inc.
Sponsor Protocol ID: AK-US-001-0102

Principle	Value
Display for 0 percentages	Blank
Display collected value	Minimum and maximum
Display 1 decimal place	Q1 (25 th Percentile), Q3 (25 th Percentile), Mean, Mean Difference, Median, Standard Deviation, and Confidence Interval for all parameters except DXA parameters.
Display 3 decimal places	Q1 (25 th Percentile), Q3 (25 th Percentile), Mean, Mean Difference, Median, Standard Deviation, and Confidence Interval for DXA parameters; p-value.
Limit of precision for displays	1 decimal place, unless otherwise specified.
Date Format	DDMMYYYY

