7.7.2 Adverse Events

Clinical and laboratory AEs will be coded using the MedDRA Version 23.1 (or a later version if updated during the study). SOC, High-Level Group Term (HLGT), High-Level Term (HLT), PT, and Lower-Level Term (LLT) will be attached to the clinical database. AE severity will be graded using the National Cancer Institute-Common Terminology Criteria for Adverse Events (NCI-CTCAE, version 5.0). The relationship between an AE and study drug will be assessed (Related/ Not related) and also the relationship to study procedures.

AEs will be classified as either pre-treatment AEs or TEAEs as follows:

- pre-treatment AEs are events that start prior to the date of first dose of study drug.
- TEAEs are events with start date on or after the date of first dose of study drug and up to 30 days after date of last dose of study drug.

Any AEs leading to premature discontinuation of study drug will be summarized separately.

CONFIDENTIAL

Document Date: 07 Feb 2024

Page 44 of 60
ST-AD-008 version 05

Statistical Analysis Plan

Sponsor Name: Akero Therapeutics, Inc.
Sponsor Protocol ID: AK-US-001-0102

An overview table will summarize the number and percentage of subjects with at least one of the following AEs, where subjects with more than one event in a particular category are counted only once in that category:

- Any TEAEs;
- Any TEAEs by maximum severity grade (a subject will be counted in only one category);
- Study drug-related TEAEs (overall and by maximum severity);
- Study procedure related TEAEs (overall and by maximum severity);
- Any TEAEs of special interest (overall, injection site reaction, diarrhea, hypoglycemia, neurological or psychiatric event, or DILI)
- Any TEAEs of decompensated liver disease events including ascites, hepatic encephalopathy (HE), or variceal bleeding;
- Any SAEs;
- Any treatment-emergent SAEs (TESAEs);
- Any TEAEs leading to premature discontinuation of study drug;
- Any TEAEs leading to premature discontinuation of study from the end of study eCRF;
- Any TEAE leading to death.

Summaries (number and percentage of subjects) will be presented by SOC and PT for each of the categories in the overview (with the exception of Any TEAEs leading to premature discontinuation of study). Common TEAEs (PTs with an incidence $\geq 15\%$ in any treatment group) will be presented by SOC and PT as well.

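### The cardiovascular comparison in SAP 7.6.3.5 uses crude proportions of all randomized subjects, so subjects who leave early without an event count as event-free for the whole period

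*SAP*

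**What the plan says.** SAP 7.6.3.5 treats the adjudicated cardiovascular endpoint as a yes/no outcome at three time points in the FAS: "urgent or emergency visits for heart failure at Week 48, Week 96, and end of study will be performed using the FAS". The comparison is a stratified test: "A CMH test will be used to compare the differences in proportions of subjects with adjudicated cardiovascular endpoints". Differences with Miettinen-Nurminen intervals, odds ratios, risk ratios and p-values follow.

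The denominator comes from three general rules:
- SAP 5.3: the analysis set "will be the FAS which will include all subjects who were randomized into the study".
- SAP 7.1, denominator for percentages: "Number of subjects in the analysis set, unless stated otherwise in table shell".
- SAP 6.2: apart from missing biopsies, "values for missing data will not be imputed unless specified". No rule covers incomplete cardiovascular follow-up.

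On follow-up, Protocol 3.3 says that after study drug is discontinued "participation will end once all study assessments and the 30-Day Follow-up visit has been completed". Protocol 3.1 requires only a 30-Day Follow-up visit after discontinuation, and Protocol 6.22 records SAEs until 30 days after the last dose. Subjects also leave for refusing the Week 24 biopsy (Protocol 6.8) and for hepatic outcome events (Protocol 6.25.1).

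The neighbouring outcome, event-free survival (SAP 7.6.3.4), uses the same FAS but is analysed by Kaplan-Meier with censoring at the last assessment.

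**The concern.** A myocardial infarction, stroke or heart-failure admission can be counted only while the subject is being followed. Under 7.6.3.5 a subject who stops at Week 8 and has no event by about Week 12 stays in the Week 96 denominator as a non-event. The reported proportion then mixes risk with length of observation.

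There are two consequences. First, the absolute 96-week risk is too low wherever there is loss, even if loss is equal across arms. Second, if loss is unequal, the risk ratio moves toward the arm observed for less time. A confidence interval shows imprecision but does not show this bias.

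Protocol 1.6 gives raised cardiovascular risk in NASH as the reason for recording and adjudicating these events, so the resulting ratios and p-values are likely to be read as safety evidence. The SAP gives no reason for censoring one outcome endpoint and not the other.

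**Working it through.** **Plan's own figure.** The documents give no cardiovascular event rate, expected event count or power for this endpoint, so there is nothing to reproduce directly. The Phase 2a disposition figures used below are internally consistent: 4 + 4 + 3 + 2 = 13 and 13/80 = 16.25%, against a stated 16.3%.

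**Inputs from the documents**
- Phase 2a discontinuations over 16 weeks (Protocol 1.4.1.1): "4 subjects in 50 mg EFX, 3 subjects in 28 mg EFX and 2 subjects in the placebo group". With group sizes from Protocol Table 1, p = 4/20 = 20.0%, 3/19 = 15.8% and 2/21 = 9.5%.
- Observation after stopping: 30 days = 30/7 = 4.29 weeks.
- Horizon: 96 weeks. Subjects per arm: 40 (Protocol 5.2.2).

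**Assumptions, not in the documents**
- A low, constant cardiovascular event rate, equal in all arms.
- Discontinuation unrelated to cardiovascular risk, with hazard h = −ln(1 − p)/16 to Week 16 and k × h afterwards, for k = 0, 0.5 or 1.
- True 96-week incidence of 5%, with 2% and 10% as a range.

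**Formula.** With S(t) the proportion still on drug, mean observed time = 4.29 + ∫S(t)dt from 0 to 91.71 weeks. The observed fraction is f = that time / 96. At a low event rate the crude proportion is about f × true risk, so a true risk ratio of 1 is reported as f(EFX)/f(placebo).

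**Worked case, k = 0 (no discontinuation after Week 16)**
- 50 mg: h = 0.01395; 0.2/0.01395 = 14.34; 0.8 × 75.71 = 60.57; (4.29 + 14.34 + 60.57)/96 = 0.825.
- 28 mg: (4.29 + 14.70 + 63.76)/96 = 0.862.
- Placebo: (4.29 + 15.23 + 68.50)/96 = 0.917.
- Reported ratios: 0.825/0.917 = 0.90 and 0.862/0.917 = 0.94.

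| Hazard after Week 16 | f: 50 mg / 28 mg / placebo | 96-week loss: 50 mg / 28 mg / placebo | Reported RR: 50 mg / 28 mg |
|---|---|---|---|
| none | 0.825 / 0.862 / 0.917 | 20% / 16% / 10% | 0.90 / 0.94 |
| half | 0.684 / 0.743 / 0.839 | 54% / 45% / 30% | 0.82 / 0.89 |
| full (extreme) | 0.584 / 0.652 / 0.772 | 74% / 64% / 45% | 0.76 / 0.85 |

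The understatement of absolute risk is 1 − f. With no later discontinuation it is 17.5%, 13.8% and 8.3% for 50 mg, 28 mg and placebo.

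**In events.** The bias for 50 mg against placebo at 5% incidence is 40 × 0.05 × (0.917 − 0.825) = 0.18 events with no later discontinuation, and 40 × 0.05 × (0.839 − 0.684) = 0.31 with half the hazard. At 2% incidence these are 0.07 and 0.12; at 10% they are 0.37 and 0.62.

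**Second check with assumed loss rates.** Numerical integration at 5% true incidence and equal hazards gives these Week 96 results:
- Loss of 20% in both arms: 4.53% in each arm. The ratio is 1.00, but both figures are below the true 5%.
- Loss of 10% placebo, 20% EFX: 4.77% against 4.53%, ratio 0.95.
- Loss of 20% placebo, 40% EFX: 4.53% against 4.01%, ratio 0.89. A true hazard ratio of 1.5 would then read 1.31.

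Week 48 shows the same effect to a smaller degree (0.98 at 10/20% loss and 0.94 at 20/40%).

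**After the fix.** Events per person-time give 2.79 per 100 patient-years in both arms in every equal-hazard scenario at 5% incidence, that is, a ratio of 1.00.

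**The case against.** The strongest reply is that the direction is unknown and the size trivial. Most of it stands.

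- **Direction.** A reader might infer that EFX will look safer than it is. The documents do not support that. Loss by arm in this trial is not given. The Phase 2a contrast is one or two subjects (Fisher p = 0.41 for 50 mg and 0.65 for 28 mg against placebo), and Protocol 1.7 reports no TEAE discontinuations on 50 mg. If the drug works, removal for progression to cirrhosis or hepatic events could cost placebo more subjects.
- **Size.** A reader might take 0.76 as the likely distortion. It requires the 16-week hazard to persist to Week 96, which means 74% loss on 50 mg. Even 0.82 requires about 54%.
- **Inference.** At 5% incidence, the chance of a significant result favouring EFX under equal hazards moves only from 1.9% (20% loss in both arms) to 2.4% (20% placebo, 40% EFX). This is from an unstratified Pearson test used as a stand-in for CMH.
- **Adverse-event tables.** A reader might extend the point to SAP 7.7.2, which says "Summaries (number and percentage of subjects) will be presented by SOC and PT for each of the categories in the overview". That is weaker. TEAEs have an explicit window of treatment plus 30 days, and SAP 7.7.1 tabulates exposure by arm.
- **Follow-up.** Vital-status searches may find late deaths (Protocol 6.19), late SAEs are reportable if considered related (Protocol 6.22.6.2), and ongoing findings are followed (Protocol 3.3). None of these reliably captures an unrelated late infarction, stroke or heart-failure admission.
- **Table shells.** The whole-set denominator is a default that a shell could override, and the shells are not in the documents. However, 7.6.3.5 itself names the FAS and mentions no censoring.

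**Conclusion.** The defect is real but minor. As written, 7.6.3.5 counts early leavers without an event as event-free to Week 48, Week 96 or end of study. The absolute risk is understated in every arm that loses subjects. The risk ratio is biased only if loss differs, and then in favour of the arm with more loss, which the documents do not identify.

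On the Phase 2a illustration, a true ratio of 1 reads 0.90 (50 mg) and 0.94 (28 mg) with no discontinuation after Week 16, and 0.82 (50 mg) with half the hazard. That is 0.2 to 0.3 events per 40-subject arm at an assumed 5% incidence. These figures rest on a constant and equal event rate, on discontinuation unrelated to cardiovascular risk, and on very small Phase 2a counts. The endpoint is exploratory and the primary conclusion is not affected. What is affected is how the cardiovascular summary reads.

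**What to change.** In SAP 7.6.3.5:
- Define time to first adjudicated cardiovascular event, censored at the earlier of last contact and the end of event collection.
- Report cumulative incidence at Weeks 48 and 96 by arm, with non-cardiovascular death as a competing event.
- Report events per 100 patient-years and follow-up time by arm.
- Keep the crude FAS proportion, labelled as descriptive.
- State that censoring assumes loss is unrelated to cardiovascular risk.

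A stratified log-rank test or hazard ratio is not needed, because with so few events it would add little. Exposure-adjusted rates in the SAP 7.7.2 overview are an optional addition.

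The cost is SAP wording and a few extra tables from data already collected, with no change to trial conduct. Reported cardiovascular risk will rise, and will rise most in arms with more loss.

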7.6.3.6 Changes from baseline in bone biomarkers

The analysis of changes from baseline in bone biomarkers will be performed using the Biomarkers Analysis Set. An MMRM model with baseline covariate will be used to evaluate the changes and percent changes from baseline in P1NP and CTX-1 between the EFX arms and the placebo arm at scheduled visits, controlling for stratification factors. LS means, 95% CIs, and p-values will be presented.

Summaries and boxplots will be presented for actual values and changes from baseline in P1NP and CTX-1 at the collection time points defined in the Schedule of Assessments by treatment group.

Statistical Analysis Plan

Sponsor Name: Akero Therapeutics, Inc.
Sponsor Protocol ID: AK-US-001-0102

7.6.3.7 Changes in cardiovascular and metabolic risk factors

The analysis of changes in cardiovascular and metabolic risk factors will be performed using the Safety Set. Descriptive summaries and boxplots of BMI and blood pressure will be presented by treatment group and visit.

An MMRM model with baseline covariate will be used to evaluate the changes from baseline in blood pressure between the EFX arms and the placebo arm at scheduled visits, controlling for stratification factors. Least square (LS) means, 95% CIs, and p-values will be presented. The analysis will be performed using the Safety Set.

A CMH test will be used to compare the differences in proportions of subjects with new onset of T2D between the EFX arms and the placebo arm, adjusting for stratification factors. The new onset of T2D is defined as a single HbA1C value of 6.5% or higher when baseline HbA1c <6.5%. The analysis will be performed using the Safety Set.

7.6.3.8 Non-invasive measures of fibrosis can predict histological regression and/or progression of fibrosis and clinical complications of cirrhosis

Correlation models will be fitted to explore the correlation coefficient between non-invasive measures of fibrosis and histological fibrosis (CRN fibrosis stage of liver biopsy) and clinical complications of cirrhosis (MELD score and CP score). Non-invasive measures of fibrosis include serum biomarkers (ELF and Pro-C3) and imaging (liver stiffness by FibroScan). In addition, correlation between the imaging marker for hepatic fat (MRI-PDFF) and histological fibrosis and NASH resolution will also be explored. The analysis will be performed using the LBAS.

